### **C. Subject Selection**

Patients potentially eligible for this study are at least 18 years of age and have active HS sites with fistula(s) or sinus tracts. A total of 20 subjects will be enrolled in the study. Potential patients will be assessed for eligibility to participate in this clinical study using the criteria for inclusion and exclusion listed below.

#### **Inclusion Criteria:**

A subject must meet all of the following criteria in order to be eligible to participate in this study:

1. Male or female subjects are at least 18 years of age or older
2. A confirmed diagnosis of HS disease
3. Presence of inflammatory HS lesion(s) and one or more fistula(s) or sinus tracts

#### **Exclusion Criteria:**

Eligible subjects will be excluded from participation if they meet any of the following criteria:

1. Receiving any other kind of treatment for fistulas including introduction of anti-inflammatory systemic therapy such as prednisone or adalimumab within the prior month.
2. Are currently pregnant or planning to get pregnant during the study.
3. Are participating in another study using an investigational agent or procedure during participation in this study.
4. Have any condition that, in the opinion of the investigator, would compromise the well-being of the subject or the study.

#### **Urine Pregnancy Test**

A urine pregnancy test will be performed locally for all females of childbearing potential at the Baseline Visit prior to the first dose of study drug and at minimum at monthly intervals (either at study visits or at home between scheduled study visits). The results of the monthly at home tests must be communicated to the site. More frequent pregnancy tests will be performed throughout the

study if required per local/country requirements.

- If the Baseline urine pregnancy test performed at the site is negative, then dosing with study drug may begin.
- If the Baseline or postbaseline urine pregnancy test performed at the site is positive, dosing with study drug must be withheld and a serum pregnancy test is required. The serum pregnancy test will be performed by the central laboratory. If the serum pregnancy test is negative, study drug may be started or resumed. If the serum pregnancy test is positive, study drug must be permanently discontinued. In the event a pregnancy test comes back borderline, a repeat test is required ( $\geq 3$  days later). If the repeat serum pregnancy test is:
  - Positive, the subject must be discontinued;
  - Negative, the subject can continue in the trial;
  - Still borderline  $\geq 3$  days later, this will be considered documentation of continued lack of a positive result and the subject can continue in the study (unless prohibited locally) in the absence of clinical suspicion of pregnancy and other pathological causes of borderline results.

If time between visits is longer than 1 month, then collect the results of the monthly at home urine pregnancy test between scheduled visits.

If during the course of the study a female becomes surgically sterile or postmenopausal and complete documentation as described in Protocol Section 5.2 (Contraception Requirements for Females) is available, pregnancy testing is no longer required.

A pregnant or breastfeeding female will not be eligible to enter the study or be allowed to continue study drug.

#### **B4. POSSIBLE BENEFITS**

The potential benefits of this study are that the individual subject's Hidradenitis Suppurativa caused fistulas and sinus tracts might improve with the administration of sclerosants like hypertonic saline.

#### **B5. POSSIBLE RISKS AND ANALYSIS OF RISK/BENEFIT RATIO**

Hypertonic saline is as effective as other sclerosants with the advantage of lack of allergenicity and low costs. The most common adverse events or risks associated with sclerotherapy using hypertonic saline are hyperpigmentation, teleangiectic matting (neovascularization), pain, ulceration and tissue necrosis. Other reported less common adverse events include exacerbation of hypertension, necrosis of kidney cortex, hemolysis, hematuria, central nervous system disorders, hyponatremia and membranous fat necrosis.

When used to treat fistulas or sinus tracts, none of the systemic adverse events are expected to occur. The common adverse events can be minimized by adhering to meticulous technique.

Risks listed in ICF are as follows:

**More Common:** Stinging, pain in the injected area

**Less Common:** Skin Ulceration,

**Rare:** Infection

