**B. Statistical Considerations**

**a. Sample Size Justification:**

The total number of subjects to be studied is 20 and the number to be studied at BIDMC is 14. A sample size calculation is not applicable, for this is an early feasibility and tolerability pilot study.

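### The consent-form risk list reported in B5 leaves out three of the five local events that B5 itself calls most common, and classes a fourth lower, without giving a reason

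*Combined protocol and SAP*

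**What the plan says.** Both lists stand in section B5 of the combined protocol and SAP.

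The narrative gives the general risk profile of the procedure: "The most common adverse events or risks associated with sclerotherapy using hypertonic saline are hyperpigmentation, teleangiectic matting (neovascularization), pain, ulceration and tissue necrosis". Two qualifying sentences follow. The first is specific to the site of injection: "When used to treat fistulas or sinus tracts, none of the systemic adverse events are expected to occur". The second concerns the local events: "The common adverse events can be minimized by adhering to meticulous technique".

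The section then turns to the consent form with the words "Risks listed in ICF are as follows" and gives three classes:

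- More common: "Stinging, pain in the injected area".
- Less common: "Skin Ulceration", followed by a comma and nothing more.
- Rare: infection, and nothing else.

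B6 (Consent) has a licensed physician explain the study's benefits and risks, and gives each subject a copy of the signed form. B6 (Subject Protection) lets patients take the form home to read. Neither part of B6 lists any risks.

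**The concern.** A reader who moves from the B5 narrative to the ICF list beneath it finds two different accounts of the local risks of the same injection. If the ICF matches the protocol's report of it, a subject relying on the written form would not learn of tissue necrosis, hyperpigmentation or matting, although the protocol counts all three among the most common events. The written form matters here because patients may take it home before deciding, and because B3 allows up to three injections per subject. What is at stake is the accuracy of the safety information given at consent.

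**Working it through.** There is no figure of the plan to reproduce. The check sets the two B5 lists side by side, item by item.

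| Event | B5 narrative | ICF list as reported in B5 | Result |
|---|---|---|---|
| Pain | most common | more common | agrees |
| Ulceration | most common | less common | lower class |
| Hyperpigmentation | most common | not listed | omitted |
| Telangiectatic matting | most common | not listed | omitted |
| Tissue necrosis | most common | not listed | omitted |
| Stinging | not named | more common | added |
| Infection | not named | rare | added |

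For the five narrative events: 1 agrees + 1 in a lower class + 3 omitted = 5. In the other direction, the ICF list adds 2 items.

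Next, does B5 supply a reason for the difference?

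1. *The site-specific sentence.* It sets aside systemic events only. Hyperpigmentation, matting and tissue necrosis are local skin or tissue events, so it does not reach them.
2. *The technique sentence.* It says that the common events can be made less frequent or less severe. That could support a lower class. It does not say that an event no longer applies, so it does not support leaving one out.
3. *Low frequency.* The ICF list extends down to a rare class, which holds infection. An event thought to be rare in tracts could have been placed there, so low frequency alone does not explain absence.

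Finally, the trailing comma. If one of the three missing events was lost from the less-common line, the omissions fall from 3 to 2 (3 − 1 = 2). The recovered event would then be in a lower class than in the narrative, so lower-class events rise from 1 to 2 (1 + 1 = 2). The number of events that do not match stays at four of five: 3 + 1 = 4 as the text stands, 2 + 2 = 4 with one item restored.

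No other section of the documents restores the missing events.

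**The case against.** The strongest defence is that the two lists answer different questions. The narrative describes hypertonic saline sclerotherapy in general, and the ICF list describes its use in tracts. B5 draws that distinction itself, and its technique sentence gives some ground for a lower class for ulceration. B5 also states no rates, so an event could be among the most common of a set and still be uncommon in absolute terms. This weakens the point about ulceration. It does not account for the three omissions, because B5 makes the tract-specific argument for systemic events alone.

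Four further limits stand:

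- The ICF is not among the documents reviewed; only the protocol's report of it is.
- The comma may mark lost text.
- A physician explains the risks orally.
- The ICF list adds stinging and infection.

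A reader might therefore infer too much by saying that subjects are told of a milder risk profile. The documents show a mismatch in the written list as the protocol reports it. They do not show what each subject is told, and the list is not milder on every item.

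A reader might also infer that the omitted events will be under-reported and tolerability overstated, since the study describes its purpose with the words "for this is an early feasibility and tolerability pilot study". The documents do not support that. The protocol available to assessors names all five events, B3 tells patients to call or visit if an adverse event occurs, and B8 requires adverse-event records. Nothing limits collection to the ICF items.

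**Conclusion.** Wrong as written: an internal inconsistency in the risk information. As the text stands, three of the five events that B5 calls most common are missing from its own statement of the ICF risks, and a fourth is classed lower, with no reason given for the omissions. The technique sentence may partly explain the lower class for ulceration.

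The conclusion assumes that B5 reports the ICF faithfully and that its text is complete. If one item was lost after the comma, two omissions remain and the lists still disagree. The documents do not settle which list is correct for tract injection. No sample size, test or estimate depends on the point; its weight lies in consent and patient safety.

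**What to change.** Reconcile the two lists in B5 and the ICF. Either the ICF carries the local events that B5 calls most common, in a frequency class consistent with B5, or B5 states for each event why it is left out or classed lower when the injection is into a fistula or sinus tract. At the same time, name stinging and infection in the narrative so that the lists agree in both directions, and check whether the less-common line is complete.

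The cost is a wording amendment to the protocol and the ICF. The IRB should decide whether subjects already enrolled need to be informed. No visit, assessment or analysis has to change.

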## **B6. RECRUITMENT AND CONSENT PROCEDURES**

### **Recruitment**

Dermatologists from Beth Israel Deaconess Medical Center will be informed using IRB-approved recruitment letters of this study and asked to refer eligible patients to our research unit. These letters will explain the purpose of the research, including a brief description of the nature and extent of involvement, and the investigator's email and phone number will be included. A research study advertisement will also be posted in the dermatology clinic.

A list of potential subjects will be compiled from [name] and [name] patient population using ICD codes for HS. These identified patients will be sent recruitment letters informing them of the study and to contact one of the doctors if they are interested.

The study will also be placed on TrialX as well as skinstudies.com, craigslist, twitter and BU quickie jobs. TrialX will use clinicaltrials.gov information; skinstudies.com, craigslist, twitter and BU quickie jobs will use the recruitment flyer and language from the targeted provider email.

We will advertise the study on Twitter as well with the following posting: "Do you have Hidradenitis Suppurativa (HS)? You may be eligible to participate in a clinical trial. If you are interested visit our website skintudies.com, email us at [[contact]](mailto:[contact]) or call at [contact]."

### **Consent**

Prior to entering the study, a licensed physician investigator will explain to the potential subject the nature of the study, its purpose, procedures, expected duration, and the benefits and risks involved in study participation. The licensed physician will explain the main study.

Subjects will be given the opportunity to ask questions and be informed of their right to study withdrawal. After this explanation and before any study-specific procedures have been performed, the potential subject may voluntarily sign and date the informed consent form for the main study, thereby giving permission for the subject to enter the study.

Prior to participation in the study, the subject will receive a copy of the signed and dated written informed consent form and any other written information provided to the subject. If, for any reason, the subject desires more time to consider the decision, the subject will be given a copy of the unsigned consent form for reference and instructed to call the office if they decide to participate in the study.

### **Subject Protection**

In order to address the issue of patients feeling pressured to participate, a standard approach was developed and implemented years ago. This gives the patient the opportunity to actively demonstrate their interest before enrolling in the study. If a discussion about the study presents itself during a clinical encounter, the patient is offered to take the consent home and read and then asked to follow up with the clinic if they are interested. It is also attempted to have a physician who is not involved in their clinical care go over their consent form in order to provide further separation.

## B7. STUDY LOCATION

### Privacy

Subject visits will be conducted in the CRC at BIDMC or, rarely, in private patient exam rooms in the dermatology clinic if the CRC is not available at the time of subject visits. Both locations should ensure adequate privacy for patients. Patients will complete all study related procedures in these private settings, including questionnaires. Questionnaires will be in written form and returned directly to the investigators or study staff.

Pre-screening telephone calls and subject visits will be limited only to the minimum amount of data necessary to accomplish the research purposes. No sensitive questions will be discussed by telephone

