### B3. DESCRIPTION OF RESEARCH PROTOCOL

#### A. Study Design – Overview, Methods, Procedures

##### Study Design and plan:

The design of this study is a single center, single-blinded clinical research treatment study. This clinical study will be conducted at Beth Israel Deaconess Medical Center in Boston (the study was previously conducted at MGH and is currently being conducted at both institutions through Cede Review with MGH as the overseeing IRB and BIDMC). All subjects with a signed informed consent will be screened to ensure they meet all inclusion criteria and do not meet the exclusion criteria. After enrolment, the duration of the study is approximately 8 weeks, involving 3 or 4 visits. A schematic overview of the main procedures during each visit is illustrated in Appendix 2.

The clinical effect of the hypertonic saline treatment will be evaluated with Physician and patients Assessments at week 2 (t=2), week four (t=4) and week 8 (t=8) and compared with the first visit (baseline) (t=0). If necessary, subjects will be eligible to receive another hypertonic saline injected in week 2 and/or week 4, with a maximum of three injections. Simultaneously improvement will be assessed by ultrasound if possible, using the Philips Lumify Ultrasound Device, and by patients using HS Improvement Assessments. Pain and stinging during treatment sessions will be monitored using numeric rating scales (NRS). For monitoring quality of life the DLQI will be used.

Prior to performing any study related procedures, the investigator will discuss with each subject the nature of the study, its requirements and its restrictions. A written informed consent form will be obtained from each participant prior to any procedure. Each subject with a signed informed consent form will be screened at the first visit, to ensure all the inclusion criteria are met and none of the exclusion criteria. Medical history and demographic information will be taken. Patients will have their medication reviewed and undergo a full HS examination, including lesion counts, Hurley staging and target site assessment. Target HS area(s) will be digitally photographed and be imaged with ultrasound. The duration of the study is approximately 8 weeks, involving a minimum of 3 and a maximum of 4 visits. In case of an adverse event or disease progression, patients are instructed to call and/or visit the clinic. An overview of the exact procedures during each visit can be found in the chart

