**b. Data Analysis:**

**Primary study parameter(s)**

The clinical efficacy will be measured by Physician and patients Assessments. These are continuous variables and depending on the date distribution a one way ANOVA, a Kruskal Wallis or a Wilcoxon rank sum test will be performed for analysis.

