**Secondary study parameter(s)**

Hence the small patient group in this pilot study, no power is expected from statistical analysis. Therefore all outcomes will be assessed by using descriptive statistics.

The clinical efficacy will also be measured using the following outcomes:

- Measuring the length and the lumen of the fistulas using ultrasound if possible. Since this variable is highly dependent on investigator and experience with ultrasound, descriptive statistics will be used to present this variable.

The patient reported outcomes:

- HS Improvement assessment: this is a continuous variable and depending on the date

distribution a one way ANOVA, a Kruskal Wallis or a Wilcoxon rank sum test will be performed for analysis.

- NRS to assess pain and stinging: continuous variable. Per individual a percentage improvement will be calculated as a main outcome.
- DLQI: continuous variable. this is a continuous variable and depending on the date distribution a one way ANOVA, a Kruskal Wallis or a Wilcoxon rank sum test will be performed for analysis.

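### Patient efficacy questionnaires may be returned straight to the investigators, and nothing in the text supplied sets the rating order or keeps patient scores from the physician rater

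*Combined protocol and SAP*

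**What the plan says.** Section B7 (Study Location, Privacy) covers how patient forms are completed and returned. On place: "Patients will complete all study related procedures in these private settings, including questionnaires". On return: "Questionnaires will be in written form and returned directly to the investigators or study staff".

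Under Data Analysis, the primary parameter is stated as "The clinical efficacy will be measured by Physician and patients Assessments". The Study Design and plan section sets weeks 2, 4 and 8 against baseline for these ratings. It adds a separate patient rating: "Simultaneously improvement will be assessed by ultrasound if possible, using the Philips Lumify Ultrasound Device, and by patients using HS Improvement Assessments". The analysis section places HS Improvement, the numeric rating scale (NRS) for pain and stinging, and DLQI among the secondary parameters.

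The design is called single-blinded, without saying who is blinded or to what. No control group is described. Section B8 gives the principal investigator, sub-investigator and study staff access to the stored, coded forms.

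**The concern.** The efficacy outcomes that carry a planned test are ratings by a person who knows that treatment was given. A patient who expects to hand a form to the doctor who gave the injection may rate more kindly than otherwise. A physician who reads the form first may move toward the patient's view. In that case, agreement between the two ratings is not independent corroboration, although a reader of the results would take it as such.

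With no described control group, a shift of this kind has nothing to cancel against and goes into the change from baseline. Recruitment makes the first mechanism plausible: the Recruitment section draws candidates partly from named clinicians' own "patient population using ICD codes for HS", so the person receiving the form may be the treating doctor.

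**Working it through.** The plan has no figure to reproduce on this point. It gives no scale, standard deviation, significance level or expected effect, and it declares a sample size calculation not applicable. The check sets the sections side by side.

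1. **Who may receive the form.** Section B7 names two recipients, investigators or study staff. Handing it to the assessing physician is allowed but not required.
2. **Order of ratings.** Study Design and plan fixes the visits, not the sequence within a visit. The part of the study table that is supplied has no row for either assessment.
3. **Whether the physician is kept unaware of the patient's scores.** No section supplied says so. Coding and a locked cabinet (B8) protect confidentiality. They do not stop a physician reading a form handed over at the visit, and B8 gives investigators access to the stored forms.
4. **Whether single-blinded supplies the safeguard.** It cannot be relied on, because the blinded party is not named.
5. **Whether separation from the treating doctor applies.** The Subject Protection section opens: "In order to address the issue of patients feeling pressured to participate, a standard approach was developed and implemented years ago". Its measures concern taking the consent form home and, where possible, having a physician outside the patient's care explain it. They do not extend to outcome ratings.
6. **Which outcomes are exposed.** HS Improvement and DLQI are patient-reported and listed as secondary. The patient part of the primary assessment is exposed too if it is collected on one of these forms. The plan names no instrument for it, so that link is likely but not stated.

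Steps 1 to 5 together leave the route open: the physician may receive the form, may read it before rating, and no stated rule prevents this.

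**The case against.** The strongest reply is that the sentence comes from a privacy paragraph that was not written to govern outcome assessment, and that the larger weaknesses lie elsewhere: a primary patient assessment with no named instrument, an undefined blind, and no described control. That is fair. Expectation, natural fluctuation and regression to the mean would also produce apparent improvement here, and an envelope removes none of them. The patient still knows that treatment was given and that the team will hold the form.

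Four stronger readings are tempting, and the documents do not support them.

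- **That forms go to the investigators.** Study staff are named as the alternative, and no section says that the physician does see the score first.
- **That the questionnaires carry half of the primary outcome.** No weights, composite or instrument are given, and the named questionnaires are secondary.
- **That a false-positive rate can be attached to the defect.** Take 20 patients, no true effect, a two-sided 5% paired t test and an assumed shift of d standard deviations of change. The noncentrality is d × √20, with 19 degrees of freedom. The chance of a false finding of improvement is 2.5% at d = 0, 13% at 0.2, 25% at 0.3 and 56% at 0.5. The arithmetic is right, but the shifts have no source in the documents. The paired test is not among those listed, which are one-way ANOVA, Kruskal-Wallis and Wilcoxon rank sum. The result would be the same for a shift from any cause, so it does not measure the return route.
- **That the plan recognises rating bias in its Subject Protection section.** That section is about pressure to take part. Applying it to ratings is an analogy.

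The text is also incomplete. Some pages were removed before review, Appendix 2 is not shown, and the study table appears cut off, so a safeguard there cannot be excluded. Pilot status limits what is at stake, but the plan still intends tests of efficacy.

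What stands is that the supplied text permits the route and states no protection against it.

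**Conclusion.** The concern holds in a limited form. The plan allows patient questionnaires to reach the investigators directly, and the text supplied neither orders the two ratings nor keeps the patient's scores from the physician rater. In a study with subjective efficacy ratings and no described control, this leaves room for courtesy bias and for a physician rating that depends on the patient's.

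The size cannot be estimated from the documents, and closing this route would remove only part of the rating bias. The conclusion assumes that no rating order or collection rule sits in the material not supplied. It is worth acting on because the change is nearly free, not because a large effect has been shown.

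**What to change.** Replace the B7 sentence on the return of questionnaires with wording to this effect:

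*At each visit the patient efficacy questionnaires (patient assessment, HS Improvement and DLQI, where scheduled) are completed before the physician's assessment. They are returned in a closed envelope to study staff, not to the assessing investigator. The physician records the physician assessment before seeing the patient's scores. The NRS for pain and stinging during treatment is exempt from this order. The investigator's clinical questioning of the patient is unaffected.*

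The exemption is needed because pain and stinging during a treatment session cannot be rated before that session.

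The cost is a few sentences of text, envelopes and a fixed order within the visit, using study staff whom B7 already names. It needs no extra patients, visits or instruments. The downside is that the assessing investigator does not see the form until the physician assessment is recorded. If Appendix 2 or the full study table already sets a rating order or collection rule, a cross-reference in B7 is enough.
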